Visit 2 (about 1 week following visit 1): If able to undergo MRI scan: The patient will return to UIC and the center for Magnetic Resonance Imaging Center UIC **[name]**. During visit 2 we will ask participants to have their brain imaged by an MRI machine for assessment of their brain structure. The imaging will be performed on GE 3T MRI research dedicated scanner (MR 750) pre- and post-intervention. Padding will ensure comfort and limit excessive motion during scanning. After a brief scout image for localization, we will acquire the following whole brain images using diffusion tensor imaging, DTI; T1- and T2-weighted imaging; and arterial spin labeling (ASL).
(time~1hour)

Image acquisition will be performed on GE 3T MRI research dedicated scanner (MR 750) pre- and post-intervention. After a brief scout image for localization, we will acquire whole brain images using diffusion tensor imaging (DTI); and high-resolution 3D T1-weighted imaging. We will determine and quantify white matter integrity (DTI-FA/MD); and hippocampal volume (T1). These are indices of alterations of brain interconnections, structure, and function, which are associated with cognitive functioning (details, table 2).

Table 2. Imaging Parameters

Technique	Purpose	Parameters (TE=echo time; TR=repetition time; BW=bandwidth; FOV=field of view; TI=inversion time)
DTI	White matter integrity (FA/MD) quantification	single-shot EPI & parallel imaging using the same 32-channel phased-array head coil; TE/TR~70/5525ms, b-values 0,1000s/mm ² , 33 directions, FOV=20cm ² , matrix 160x160, NEX 2, parallel imaging acceleration factor 2; 6 B0 images, Slice thickness 3 mm
T1/BRAVO	Hippocampal Volume Quantification	Coronal; TI=4.5, Flip=13°, 1.5mm slice thickness, no gap, BW=±25kHz, FOV=22cm ²
T2-FLAIR	White matter hyperintensity quantification	Coronal; TE/TR=104.5/9500ms, TI=2.5sec, FOV 22cm ²
ASL	Cerebrovascular perfusion Cerebral blood flow	axial; Spiral-FSE acquisition; post-label delay time = 1.8 sec, TE/TR=minimum, flip angle=90°, slice thickness = 3-5 mm, matrix size = 128x128, FOV 22cm ²
Resting-state fMRI	Resting state networks	Subjects will be instructed to keep their eyes open, focus on a fixation point, and “not think of anything in particular”. Resting-state data will be acquired: total scan time = 8 minutes.

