Image Analyses DTI: FSL with TBSS, we will quantify FA and MD from whole brain and tract specific white matter. T1/FSPGR: Using FreeSurfer, we will extract hippocampal volumes (right and left) as well as sub-fields of the hippocampus adjusted for intracranial volume. T2-FLAIR: Using standard software, we will quantify white matter hyperintensity volumes across the entire brain white matter. We will use a seed-based approach to measure resting state networks of interest. *Functional connectivity networks*: Functional brain networks will be generated using the resting-state fMRI toolbox, CONN (<http://www.nitrc.org/projects/conn>); (Whitfield-Gabrieli and Nieto-Castanon, 2012)). In brief, raw EPI images are realigned, co-registered, normalized, and smoothed before analysis. Any confound effects from motion artifact, white matter, and CSF are regressed out of the signal. Using the same label maps as the structural brain networks, functional brain networks will be derived using pairwise BOLD signal correlations.

The total estimated time during visit 2 is 1-2 hours.

Visit 3. (about 1 week following visit 2): During this visit we will assess vascular health (arterial stiffness, endothelial function, and carotid artery compliance).

Participants will be asked to come back to the college of nursing in the morning between 7-11:00 am following an overnight fast with no caffeinated or sugary beverages in the morning of the test. This is done to avoid any diurnal variability. Following a 15-minute supine rest will assess several vascular health indices listed below:

Arterial Stiffness will be measured using carotid-femoral pulse wave velocity following standard procedures:

1. A blood pressure cuff is placed around the upper arm and is automatically inflated and deflated for determination of blood pressure and for pulse wave form analysis. This is similar to a usual blood pressure assessment during a clinical visit.
2. A blood pressure cuff will be placed around the upper thigh of the subject and a hand-held tonometer (similar to the eraser end of a pencil) will be placed over the carotid (neck) artery. Once the tonometer detects a carotid pulse the blood pressure cuff is inflated (similar to a blood pressure obtained in a clinical visit, but on the upper thigh) and the pulse wave form is automatically collected. This measure will be repeated 3 times and the average pulse wave velocity will be used. Total time=10 minutes

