Upon completion of Visit 3, the patient will be randomized to the 24-week walking program or usual care. The randomization will be assignment by chance using a 1:1 chance of being assigned to the exercise group over the usual care group. Participants cannot choose which exercise group they will be in. The assignment is done by a randomized numbers table in computer program that acts like flipping a coin to decide which group they will be placed in.

The total estimated time during visit 3 is 1-2 hours.

The exercise training group will participate in an educational session on walking exercise for CKD during visit 2. Participants will receive a packet of information previously developed by the PI with exercise prescription and information, and a heart rate monitor that monitors the exercise. The documents handed out to the exercise group are titled "Exercise Recommendations" and "work effort scale". We will work with the participant to 1) set up a schedule that

fits with the participant's schedule for home-based exercise; 2) identify time-slots for exercise; 3) work with the participants to assess their readiness to do exercise; 4) address perceived barriers to exercise, and 5) build a relationship with the participants to provide support and address concerns. This will be done to empower participants to take individual control of the exercise program. Participants will be asked to exercise (a brisk walk) at home, 3 times per week, for 30-60 minutes for 24 weeks.

Participants randomized to the exercise group will be contacted via phone biweekly or more frequently if they are slightly behind the exercise routine, and we will meet with them once per month to provide encouragement and progression of exercise, and to download the heart rate monitor. Participants will have the option to upload their physical activity remotely if they prefer, but they will still be asked to meet in person as scheduled. This system will allow us to monitor and address any issues to achieve optimal compliance to the intervention. We have successfully conducted this type of partially supervised exercise program in CKD patients with excellent adherence and compliance rate (80-87%).

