The monthly meetings (once per month) will occur at months, 1, 2, 3, 4, and 5 following randomization. The PI and study staff will continue to work with the participants to assess their readiness to do exercise; 2) address perceived barriers to exercise, and 3) provide support and address concerns related to the exercise program. The meetings will last 30 minutes. We will assess for any adverse events during the bi-weekly phone calls using the document title "Adverse Event Monitoring". The total number of visits in the exercise group is 11.

Usual medical care control group

The usual care group will receive standard instructions on exercise for patients with kidney disease. These documents are titled "Exercise Recommendations" and "work effort scale". This is similar to what is commonly done in clinical practice. The control group will not receive an exercise prescription or heart rate monitor. Participants will be contacted via phone biweekly to answer any questions and ensure continued study participation. In order to minimize any feeling of disenfranchisement in the control group we will offer them the exercise training prescription following all post-test data collection procedures. The usual care group will NOT meet monthly. We will assess for any adverse events during the bi-weekly phone calls using the document title "Adverse Event Monitoring". The total number of visits for the usual care group is 5.

Ten participants with an eGFR of >60 ml/min will only undergo baseline testing and not partake in the intervention or follow up. We will ask if the participants with an eGFR >60 ml/min prefer to only to the baseline versus intervention.

Follow-up testing will occur at 24 weeks over 2 visits about 1 week apart. During the follow up testing we will ask participants to perform one 6-minute walk test and the short physical performance battery, and the NIH toolbox measures as described above, as well as completing the questionnaires and imaging procedures described above.

During the 24-week visit we will query patients using structured interviews and open-ended questions as to whether participants liked the independent home-based walking program. Study satisfaction will be assessed using a likert scale and open-ended question at the end of the 24 week follow up test..

Physical activity and exercise monitoring and Assessment of Adherence to Exercise Rehabilitation Program (fidelity of treatment):

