7.0 Expected Risks/Benefits

Risk associated with the medical history assessment

Discomfort could be felt by participants when answering questions about their medical history.

Risk associated with the physical function battery

There is a slight risk of falling during the balance testing.

Risk associated with the 6 minute walk

There is a slight risk of abnormally high blood pressure, shortness of breath, muscle injury, and muscle soreness. The risk of serious adverse events with maximal exercise testing has been estimated to be 0.5 per 10,000 tests (Stuart, 1980 Chest), the risk of death associated with a 6-minute walk is currently not known, but is considered minimal risk. The exercise test (6 minute walk) proposed in this study is considered no more than usual activity of daily living and is considered moderate intensity exercise. There is a risk that underlying disease may be uncovered during study participation. This would most likely be undiagnosed cerebrovascular disease, previous stroke or mini-stroke. These findings would be immediately related to the patient and the providers (upon patient approval). These findings may require additional testing and procedures as deemed necessary by the patient's provider.

Risks associated with the walking exercise training

There is a slight risk of injury associated with exercise training in a sedentary population. There is a slight risk of abnormally high blood pressure, shortness of breath, muscle injury, and muscle soreness associated with exercise training in a sedentary (not used to exercise) population. The risk of serious adverse events with maximal exercise testing has been estimated to be 0.5 per 10,000 tests (Stuart, 1980 Chest), the risk of death associated with walking exercise training is currently not known, but is considered minimal risk. The exercise training proposed in this study is considered no more than usual activity of daily living and is considered moderate intensity exercise. There is a risk that underlying disease may be uncovered during study participation. This would most likely be undiagnosed cerebrovascular disease, previous stroke or mini-stroke. These findings would be immediately related to the patient and the providers (upon patient approval). These findings may require additional testing and procedures as deemed necessary by the patient's provider.

Risks associated with the venipuncture (blood draw)

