The blood draw may cause pain and bruising. There is a slight risk for infection, lightheadedness and fainting.

Risk associated with the cognitive function questionnaires.

There is a slight risk that participants will feel uncomfortable with filling out the questionnaires. Participants could find answering the questions boring and/or tiring. We will monitor the progress and allow participants to take breaks as needed. If they become upset or uncomfortable, they may skip a given question.

Risks associated with the MRI:

The MRI does not use x-ray radiation or radioactive material. The magnetism of the machine attracts certain metals, which could put participants at risk. Therefore, people with pacemakers, infusion pumps, metal prostheses, metallic-backed transdermal patches or metallic shrapnel will be excluded from the study. A checklist will be completed that addresses issues of MRI safety. Some people may feel somewhat closed-in (claustrophobic) during the MRI procedure. The MRI scans can get quite noisy and this may cause some discomfort. We will provide padding, a blanket, and ear plugs to ensure comfort. This risk is minimized by careful screening by qualified research personnel prior to entry into the MRI room. Subjects with metal implantations will not be recruited. Participants' can withdraw at any time and we will closely monitor them to ensure safety and comfort.

Risks associated with ultrasound procedure:

There could be pressure felt on the neck from the hand-held tonometer, which might make participants feel uncomfortable. The inflation of the blood pressure cuffs might feel too tight and cause discomfort (similar to that of having a blood pressure measured in clinic).

The blood pressure cuff could feel too tight and it may cause discomfort and pain.

There might be pressure on the neck from the ultrasound Doppler transducer, which could feel uncomfortable

If any of these occur the measurement will stop immediately.

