11.0 Data and Safety Monitoring

Serious adverse events will be monitored and tracked at each follow-up period and biweekly phone calls. Patients will be queried at the biweekly phone calls and at 24 weeks if they have had any visits to the emergency department or hospitalizations (see attached checklist). We will also ask if they have had any symptoms of cardiac-related problems such as chest, arm or jaw pain while exercising or not exercising. Data will be recorded on an excel spreadsheet and reviewed by the PI at weekly study meetings. Any unanticipated adverse events or problems will be reported to the IRB within 7 days on notification. [name], ATC, FSVM, FAHA will monitor safety data. Subjects are free to withdraw from the study at any time. If a subject withdraws from the study we will ask the subject (only once) if they are willing to come back for the follow-up tests. If the subject does not want to complete the study, no further contact attempts will be conducted and the subject will be discontinued from the study (this will be reported at the annual continuing review).

This study is funded by the Midwest Roybal Center for Health Promotion and Translation and is required to follow their NIH approved DSMB plan outlined below: The PI will be responsible for ensuring participants' safety on a daily basis. The Safety Officer (SO; [name], Roybal PI) in conjunction with a Data Safety Monitoring Roybal Center Committee will act in an advisory capacity to the NIA Director to monitor participant safety, evaluate the progress of the study, to review procedures for monitoring the confidentiality of the data, the quality of data collection, management, and analyses.

Safety Officer Membership and Affiliation.

[name], Midwest Roybal grant PI, has accepted the position as the Safety Officer and will work with the study PI to review pilot study data and safety monitoring.

Title: Co-Director, Center for Research on Health and Aging and Professor, Community Health Sciences

Organization/Affiliation: Institute for Health Research and Policy and School of Public Health, UIC

Data Safety Monitor Committee

[name] will serve as chair of the committee, and as SO for any adverse event reports. Other members will include [name] (Kinesiology), [name] (Medicine), and [name] (School of Public Health)

Conflict of Interest for SO.

The SO and DSM committee will adhere to the Conflict of Interest Policy and procedures of the University of Illinois.

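### Adverse event questions start only after randomisation and stop with the 24-week follow-up, so the ten baseline-only participants are never asked and delayed harm after the last visit has no scheduled query

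*Combined protocol and SAP*

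**What the plan says.** **When adverse events are asked about.** Section 11.0 says: "Serious adverse events will be monitored and tracked at each follow-up period and biweekly phone calls". The same section places questions on emergency department visits and hospital stays at the calls and at 24 weeks. Its closing paragraph gives the call interval as two weeks and adds a question on falls. Section 6.0 places use of the Adverse Event Monitoring form at the calls.

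**Who is called.** Section 6.0 describes the calls within the two randomised arms only. For one arm: "Participants randomized to the exercise group will be contacted via phone biweekly". The usual care arm has the same interval.

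**When that begins.** Section 6.0: "Upon completion of Visit 3, the patient will be randomized to the 24-week walking program or usual care".

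**Who is outside it.** Section 6.0: "Ten participants with an eGFR of >60 ml/min will only undergo baseline testing and not partake in the intervention or follow up". Participants with eGFR above 60 are asked whether they prefer this option to the intervention.

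**What the tests may cause.** Section 7.0 lists risks by procedure. For the blood draw, besides pain and bruising: "There is a slight risk for infection, lightheadedness and fainting". For the physical function battery: "There is a slight risk of falling during the balance testing". For the 6-minute walk it names muscle injury and soreness, among others.

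**The concern.** Several of the listed harms (bruising, infection, muscle soreness or injury) can appear after the participant has gone home, when observation during the test cannot detect them. A count of such events depends on someone asking. The description of visits 1 to 3 contains no adverse event question, and the calls begin only once a participant is in an arm.

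Three consequences follow. Randomised participants are first asked some weeks after the baseline tests and must recall over that period. Baseline-only participants are not asked at all. Nobody is asked after the last follow-up visit.

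The Safety Officer report must cover adverse events, and the monitoring committee must weigh participant risk against benefit (Section 11.0). For procedure-related events in these windows, a report of none could mean that none occurred or that nobody asked. Reporting deadlines do not close the gap. The 24-hour notice to the Safety Officer (Section 11.0) and the 48-hour notice to the IRB (Section 13.3) both run from the time staff learn of an event. Data not collected cannot be recovered at analysis.

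**Working it through.** **Inputs**
- Visit 1 to visit 2, Section 6.0: "Visit 2 (about 1 week following visit 1", so 1 week.
- Visit 2 to visit 3, Section 6.0: "Visit 3. (about 1 week following visit 2", so 1 week.
- Randomisation at the end of visit 3; intervention of 24 weeks (Section 6.0).
- Follow-up testing at 24 weeks over two visits about 1 week apart (Section 6.0).
- Calls every two weeks (Section 11.0). The date of the first call is not given. I take 2 weeks after randomisation and show 1 week as the alternative.
- Participation of 27 weeks (Section 3.0).

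**Step 1. Reproduce the plan's own figure.** With visit 1 as week 0, visit 2 is week 1, visit 3 and randomisation are week 2, the first final visit is week 2 + 24 = 26, and the second is week 26 + 1 = 27. The total, 1 + 1 + 24 + 1 = 27 weeks, matches Section 3.0. The usual care visit count also matches: 3 baseline + 2 follow-up = 5. The stated duration therefore leaves no room for a contact after the second final visit.

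**Step 2. Lag from each baseline visit to the first scheduled query.** Lag = week of first call − week of visit.

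| Visit (main procedures) | Week | First call at week 2 + 2 = 4 | First call at week 2 + 1 = 3 |
|---|---|---|---|
| 1 (blood draw, performance battery, 6-minute walk) | 0 | 4 weeks | 3 weeks |
| 2 (MRI) | 1 | 3 weeks | 2 weeks |
| 3 (vascular tests, NIH Toolbox cognitive and motor measures) | 2 | 2 weeks | 1 week |

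**Step 3. Baseline-only participants.** They are in neither arm and have no follow-up, so the number of scheduled adverse event queries is 0 for each of 10 people. The documents do not say whether the ten fall within the 72 of Section 1.0. If they do, the share is 10/72 = 14%. If they are additional, it is 10/82 = 12%.

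**Step 4. End of participation.** A harm from the first final visit (week 26) can be raised at the second (week 27). A harm that appears after week 27 has no later query. Section 6.0 names the walk test, performance battery, NIH Toolbox, questionnaires and imaging for follow-up. It does not state a repeat blood draw, so the relevant listed risks there are mainly those of walking and balance testing.

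**The case against.** The strongest case against the point is that the plan is less silent than a quick reading suggests.

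- **Monitoring during tests.** Section 1.0 provides for heart rate and blood pressure monitoring throughout testing, and Section 7.0 stops a vascular measurement if it causes discomfort. A fall in balance testing, or a faint at the blood draw, would mostly happen in front of staff. This stands. A reader might infer that baseline-only participants have no safety contact, but the documents do not support that. What they lack is a scheduled query and any contact after baseline.
- **Final testing.** A reader might infer that harms of final testing are never asked about. The 24-week questions and the two-visit schedule contradict that, although the plan does not say at which final visit, or when within it, the questions come. Only delayed harm after the last visit is clearly outside the schedule.
- **Four weeks.** A reader might apply a four-week lag to all baseline testing. It fits visit 1 only and assumes a first-call date. The questions also look back in time, so a late question need not lose the event.
- **Event-driven reporting.** Serious events are to reach the investigator promptly and then the Safety Officer, regardless of arm or call. This stands for serious events that staff learn of.
- **Tolerability.** A reader might think the trial claims to show that the test battery is tolerable. It does not. Sections 9.0 and 12.0 name recruitment, adherence and retention as the feasibility measures, and calling the procedures minimal risk is not such a claim.
- **Unseen attachments.** The Adverse Event Monitoring form and the checklist are not in the text, so their recall period is unknown. Section 6.0 nevertheless places the form's use at the calls.

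None of this supplies a question to the ten baseline-only participants or one after the last visit.

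**Conclusion.** The point holds as a gap in ascertainment, not an absence of safety oversight. Scheduled questioning runs from the first call after randomisation to the 24-week follow-up. Ten participants have none. For randomised participants the first question comes about 4, 3 and 2 weeks after visits 1, 2 and 3, or 3, 2 and 1 weeks if the first call is a week earlier. Delayed harm after the last visit is unasked for everyone who completes follow-up.

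The events at risk of being missed are mainly delayed, non-serious or simply not volunteered. The plan rates the procedures as minimal risk, so this is a cheap improvement worth making and not a fundamental flaw. The conclusion rests on the assumed date of the first call (for the lags only) and on the unseen attachments not scheduling further queries. The result for the baseline-only group does not depend on the call date.

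**What to change.** In Section 11.0:

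1. State that adverse event collection starts at consent.
2. Complete the existing Adverse Event Monitoring form at the start of visits 2 and 3, each covering the preceding visit, and at both 24-week visits.
3. Make one short closing call: about 1 week after visit 3 for baseline-only participants, and after the last follow-up visit for randomised participants. Exempt those who withdrew and declined the follow-up tests, because Section 11.0 rules out further contact with them.
4. Include the baseline-only participants in the Safety Officer report.

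The cost is a few minutes per visit and one short call per participant by current staff. The form already exists and no visit is added. The closing call would extend contact slightly past the second final visit, so the 27-week duration in Section 3.0 should be checked against it.

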1. Adherence to the exercise program in the intervention group will be tracked using a heart rate monitor. The heart rate monitor will track when exercise training has been performed (date), duration of the exercise, and the intensity of the exercise. These data will be downloaded at each monthly visit to assess adherence to the program (this is coded data). Adherence and volume of exercise will be calculated as number of exercise sessions performed divided by number of prescribed exercise session x 100.
2. We will also ask all participants regardless of group assignment to wear the lightweight accelerometer worn on the hip (Actigraph GTX3, Actigraph) for 7 days at weeks 6, 12, 18, and 24 following randomization. Participants will be mailed the actigraph and reminded to wear it during the biweekly phone calls. They will be asked to return the actigraph after 1 week using a stamped self-addressed return envelope. This is done to assess daily physical activity and is not an intervention.⁵⁶

The study manager will be trained and checked off by the PI in the measurement of the 6-minute walk and short physical performance battery. Fidelity and competence will be continuously monitored by the PI and protocol fidelity will be ascertained during bi-weekly phone calls and the once per month visits.

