8.0 Data Collection and Management Procedures

Results from all measurements, and questionnaires will be recorded on coded source documents before being entered into the electronic database that is password protected and housed on a secure CON server that only the PIs and statistician have access to. Source documents will be stored in a locked file cabinet in a locked office that only the PIs have access to. coded exercise data from the heart rate monitor and actigraph will be downloaded at each follow-up

visit to a password protected secure CON server and analyzed before being entered into the main database as described above.

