9.0 Data Analysis

[name] of the College of Nursing statistician will conduct all analyses. The apriori stated analysis is listed below.

This is a pilot study for feasibility. For these pilot data we will emphasize descriptive statistics such as means, standard deviations, effect sizes, medians, interquartile ranges, frequencies, and percentages to demonstrate the feasibility of recruitment, adherence, and retention, treatment effects over time, and proof of concept. Our statistical approach for a full trial of these hypotheses will be Generalized Linear Mixed Models (GLMM) with an identity link function for a continuous outcome or a logit link function for a binary outcome. Conceptually, GLMM is a more advanced version of repeated measures ANOVA that can account for potential correlation among multiple measurements over time while having flexibility in fitting outcomes with different distributions (such as normal, binomial or Poisson, etc.). One advantage of this approach over repeated measures ANOVA is that there is no assumption that participants are measured at every, or even the same, time points. Therefore, these models are very flexible at handling missing data. Participants who have a missing observation are not excluded, thus, this produces the intention to treat (ITT) full information maximum likelihood (FIML) model. Conducting these models on pilot data help with sample size calculations for a future R01 submission.

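### Exercise volume is calculated with the same session ratio as adherence, so it repeats adherence and leaves out the session duration that is recorded

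*Combined protocol and SAP*

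**What the plan says.** The formula is in Section 6.0, item 1 of the part on monitoring physical activity and adherence, whose heading presents it as treatment fidelity. It reads: "Adherence and volume of exercise will be calculated as number of exercise sessions performed divided by number of prescribed exercise session x 100". Earlier in the same item the plan says what the device captures: "The heart rate monitor will track when exercise training has been performed (date), duration of the exercise, and the intensity of the exercise".

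The prescription is given earlier in Section 6.0 as a range: "Participants will be asked to exercise (a brisk walk) at home, 3 times per week, for 30-60 minutes for 24 weeks". It may change over time, because for the exercise group "we will meet with them once per month to provide encouragement and progression of exercise, and to download the heart rate monitor".

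Section 8.0 says that "coded exercise data from the heart rate monitor and actigraph will be downloaded at each follow-up" visit and analysed before entry into the main database. It describes no calculation of volume. Sections 9.0 and 12.0 say that descriptive statistics will be used "to demonstrate the feasibility of recruitment, adherence, and retention"; volume is not in that list. No other section of the available text defines volume.

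**The concern.** Sessions performed over sessions prescribed is a sound adherence measure. Volume, in the ordinary sense of how much exercise was done, depends on how long the sessions lasted as well as how many there were. A formula without duration cannot separate a participant who walks for 30 minutes from one who walks for 60. An analyst following the text would report the same percentage twice under two names.

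At stake is the description of the exercise delivered. This is a pilot meant to inform a full trial, and the amount of walking achieved helps in reading either a positive or a null signal. The stated volume figure adds nothing to adherence for that purpose and can misdescribe the amount.

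**Working it through.** The plan states no volume figure to reproduce, so the check is direct arithmetic on its formula.

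**Inputs (Section 6.0).** 3 sessions per week; 24 weeks; 30 to 60 minutes per session; score = 100 × sessions performed / sessions prescribed. Sessions prescribed = 3 × 24 = 72. The documents fix no single reference length, so 30, 45 and 60 minutes are used; 45 is an assumption (the midpoint).

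**1. Identity.** Adherence and volume share numerator and denominator, so they are equal for everyone: 36 sessions give 50.0% for both, 58 give 80.6%, 72 give 100%.

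**2. When the ratio is right as a percentage of prescribed minutes.** With s sessions performed at mean length p, and 72 prescribed at mean length q:

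- percentage of prescribed minutes = 100 × (s × p) / (72 × q) = (100 × s / 72) × (p / q).

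This equals the plan's score only when p = q. Two assumed examples, with 36 sessions prescribed at 30 minutes and then 36 at 60, a total of 1,080 + 2,160 = 3,240 minutes:

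- All 72 walked as prescribed: score 100%; minutes 3,240 / 3,240 = 100%. The two agree, although session length is not constant.
- Only the first 36 walked, each as prescribed: score 50%; minutes 1,080 / 3,240 = 33.3%. The two differ, although no session was cut short.

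**3. Spread at a fixed score.** For 72 completed sessions, all scored 100%:

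- 72 × 30 = 2,160 minutes (90 per week)
- 72 × 60 = 4,320 minutes (180 per week); ratio 4,320 / 2,160 = 2.0

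As a percentage of prescribed minutes, this span is:

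| Reference length | Prescribed minutes | All sessions 30 min | All sessions 60 min |
|---|---|---|---|
| 30 min | 2,160 | 100% | 200% |
| 45 min (assumed) | 3,240 | 66.7% | 133.3% |
| 60 min | 4,320 | 50% | 100% |

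**4. Order of participants.**

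- 36 × 60 = 2,160 minutes (90 per week): score 50%.
- 58 × 30 = 1,740 minutes (72.5 per week): score 80.6%.

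The participant with more minutes has the lower score. If both had been prescribed 45 minutes, the percentages of prescribed minutes would be 2,160 / 3,240 = 66.7% and 1,740 / 3,240 = 53.7%, the reverse of the scores. If instead the first had been prescribed 60 minutes and the second 30, they would be 2,160 / 4,320 = 50% and 1,740 / 2,160 = 80.6%, which match the scores. The reversal in absolute minutes needs no assumption about prescription; the reversal in percentage of prescription assumes a common prescribed length.

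**The case against.** The best defence is that the formula is a percentage of what was prescribed, and the prescription is a range. Someone who completes 72 sessions of 30 minutes and someone who completes 72 of 60 have both met it, so 100% is defensible for each. The participant packet, which is not in the available text, may set individual minutes, and then some apparent reversals vanish, as step 4 shows. This part stands. It limits the two-fold figure to a worst case in absolute minutes and makes the reversal in percentage terms conditional. It does not rescue the formula as a measure of volume, because even with individual minutes known the ratio is right only when mean performed and mean prescribed lengths agree.

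A second defence is that duration is not thrown away: the monitor data are downloaded monthly and Section 8.0 has them analysed. That is true, and it makes loose drafting as likely as a deliberate choice. But Section 8.0 supplies no volume calculation, and the only stated rule is the session ratio. The hip accelerometer does not fill the gap either; it is worn for 7 days at weeks 6, 12, 18 and 24 to assess daily activity, not total training volume.

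A third is that little depends on the figure. That is correct and sets the severity.

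A reader might also infer that the ratio can be right only if each participant keeps one fixed session length. The first example in step 2 shows that this goes too far.

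**Conclusion.** The point holds as a minor error in a stated rule. On the text alone, volume equals adherence for every participant and recorded duration does not enter it. The size depends on session lengths that are not yet known: at most two-fold in absolute minutes at the same score while sessions stay within 30 to 60 minutes, and about 33% either way against the assumed 45-minute reference.

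A reader might infer that the exercise dose will in fact be misstated two-fold, or that the adherence result or the comparison between arms is compromised. The documents support neither. The two-fold figure needs participants at opposite ends of the range. The adherence ratio is usable as it is, the randomised comparison does not use the volume figure, and the named feasibility results are recruitment, adherence and retention. Nor is information lost, since duration is recorded. The consequence is confined to the descriptive report of fidelity and dose.

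**What to change.** Keep the session ratio and label it adherence only. Define volume separately as recorded minutes per participant from the heart rate monitor, in total and per week, summarised by median and interquartile range. If a percentage is also shown, use the minutes prescribed to that participant as the single stated denominator where these are recorded; otherwise report minutes only. Offering both 2,160 and 4,320 as denominators would bring the two-fold ambiguity back.

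The cost is one or two lines of definition and slightly more analysis, using data already downloaded each month. Design and participant burden do not change, and no change to the exercise prescription is implied. The new figure may look more or less favourable than the session ratio, which is a reason to fix the definition before the data are examined.
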